Following complete PD stone removal, patients will be given a validated quality-of-life instrument, the PANQOL¹⁸, at 1, 3, 6, 12, 18, and 24 months post-treatment. Similarly, the visual analog scale will also be given at 1, 3, 6, 12, 18, and 24 months post-treatment. Lastly, daily opiate use will be recorded at 1, 3, 6, 12, 18, and 24 months post-treatment. The 1, 3, 6, 12, 18, and 24-month assessments will have a ± 2 weeks window to be completed.

In order to ensure that subjects respond to the questionnaires as required, REDCap will be programmed to automatically send three reminders to the participants' email when the questionnaires are due. Furthermore, the study coordinator will make three separate attempts to contact non-responding patients within the designated timeframe. If a patient remains unresponsive, these instances will be documented as protocol deviations.

Documentation on interventions for chronic pancreatitis occurring outside of scheduled appointments will be recorded a separate CRF ("non-scheduled chronic pancreatitis interventions"). This CRF will encompass any pancreatic interventions (other than POP x ESWL planned visits) taking place between the subject's consent form signature and their final follow-up.

All patients will have a HgbA1c and fecal elastase drawn at baseline (within 12 months prior to treatment initiation) and at the 1-year mark from treatment completion. Laboratory tests will be drawn per standard of care, and tests results will be added to the REDCap database.

Figure 1: Study Flowsheet

4. Subject Inclusion and Exclusion Criteria

4.1 *Inclusion Criteria:*

1. Subjects aged 18-89
2. Subjects with abdominal pain secondary to chronic calcific pancreatitis and main pancreatic duct stones found on cross-sectional imaging, EUS, or ERP with upstream PD dilation
3. Main PD stones in the head or body that are greater than 50% in size of the immediate downstream diameter of the pancreatic duct
4. Stones ≥ 5 mm in diameter or impacted in the main PD on cross-sectional imaging or EUS

4.2 *Exclusion Criteria:*

1. Subjects who have previously received PPL or ESWL for PD stones within 12 months of enrollment
2. Patients with PD stones isolated in the tail or side branches of the main duct
3. Pancreatic tail stones comprising more than one-third of the stone burden within the main PD, if multiple locations of stones are noted within the main PD
4. Nontraversable ansa loop with upstream stones

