Statistical Analysis: Comparison of technical success rate, defined as the rate of complete clearance of PD stones, between PPL and ESWL will be performing using the chi-squared test or Fisher's exact test. Secondary outcomes including adverse event (both overall and serious adverse event) rates, procedure length, and number of procedures will be compared using a chi-square test or Fisher's exact test for categorical variables and the Student's t test will for continuous variables. A p value <0.05 will be considered significant. In the primary analysis, all results will be analyzed under an intention-to-treat protocol. A per-protocol (secondary) analysis will also be performed where the technical success will be attributed to the combination of modalities resulting in achieving the primary outcome should cross-over occur.

To identify predictors for technical success, a multivariable logistic regression will be performed incorporating variables that were associated ($p<0.2$) with technical success on univariate analysis.

In terms of secondary outcomes, change in PANQOLI scores, VAS scores, and opiate daily doses will be compared between subjects in the PPL group and ESWL group. Additional outcomes to be measured include stone recurrences and number of chronic pancreatitis-related hospitalizations during the follow-up period. Should cross- over occur, under the primary (intention-to-treat) analysis, the outcomes will be attributed to the initially randomized intervention. In the secondary (per-protocol) analysis, the outcomes will be attributed to the combination of treatments resulting in technical success. A subgroup analysis will also be performed on patients who achieved only partial stone clearance (thus considered a treatment

failure) in the above-mentioned outcomes. Comparisons will be made using a chi-squared test or Fisher's exact test for categorical variables and the Student's t test for continuous variables. Paired t tests will be performed to evaluate individual changes within each arm. A p value <0.05 will be considered significant.

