Power analysis: A large meta-analysis by Moole et al found a complete stone clearance rate of 70% in patients who received ESWL in conjunction with ERCP.¹⁴ In contrast, the largest studies examining pancreatoscopy-guided lithotripsy methods have found complete stone clearance rates ranging from 83-99%.^{6,17} Using a conservative stone clearance rate of 90% for pancreatoscopy- guided lithotripsy, a sample size calculation was performed using a two-sided test with 80% power and significance (α) of 0.05. This demonstrated the need for 124 subjects total, with 62 in each arm. Accounting for an expected dropout rate of 20%, the sample size needed would be a total of 150, or 75 subjects in each arm.

10. Data and safety monitoring plan

A Data and Safety Monitoring Board (DSMB) will be established to monitor the data and safety of this project. A DSMB will be appointed by the study team and will include at a minimum: A senior faculty member clinician with substantial research experience within the Division of Gastroenterology and Hepatology at the University of Colorado who is not involved in the study, and will serve as the group leader, a statistician, and a senior gastroenterologist from a non- participating academic institution. The DSMB will meet every six months. DSMB meetings will be only open to designated DSMB staff and other individuals who have been approved to have access to unblinded data. Any recommendations for alteration or termination for part or all of the trial shall be based on consideration of the accumulating data in the context of totality of evidence. Specific statistical monitoring guidelines for safety and efficacy concerning the primary and secondary endpoints will be developed in cooperation with the DSMB.

10.1 *Definition of AEs, serious AEs, and unanticipated problems*

AEs are defined as any undesired, harmful, or pathological change in a patient as indicated by signs, symptoms, or laboratory changes that occur in association with the use of the trial interventions, whether considered intervention-related or not. This definition includes intercurrent illness or injuries, exacerbation of existing conditions, psychological events, psychosocial events, and AEs as a result of the study intervention. All endoscopic AEs will be defined and classified as recommended by the American Society for Gastrointestinal Endoscopy (ASGE).²⁰

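### Change in PANQOL, VAS and opiate dose is labelled intention-to-treat but is tested on observed cases only, with no method for missing scores; precision is lost and any bias has an unknown direction.

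*Combined protocol and SAP*

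**What the plan says.** **Analysis set and method (Section 9, Data Analysis Plan).** The general rule is "In the primary analysis, all results will be analyzed under an intention-to-treat protocol". For the patient-reported and opiate outcomes, "change in PANQOLI scores, VAS scores, and opiate daily doses will be compared between subjects in the PPL group and ESWL group", and the method is "Comparisons will be made using a chi-squared test or Fisher's exact test for categorical variables and the Student's t test for continuous variables". Within each arm, paired t tests are added. Intention-to-treat is explained only in relation to cross-over, where "the outcomes will be attributed to the initially randomized intervention". No imputation, repeated-measures model, missing-data sensitivity analysis or comparison visit is given.

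**Collection (Section 3, Sample and Methodology).** There are six assessments, at 1, 3, 6, 12, 18 and 24 months. To limit non-response, "REDCap will be programmed to automatically send three reminders to the participants' email when the questionnaires are due", and the coordinator makes three contact attempts. After that, "If a patient remains unresponsive, these instances will be documented as protocol deviations".

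**Who is surveyed.** Section 3 ties the PANQOL to success: "Following complete PD stone removal, patients will be given a validated quality-of-life instrument". Section 9 nevertheless plans a subgroup analysis of these same outcomes in patients with only partial clearance.

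**Dropout (Section 9, Power analysis).** "Accounting for an expected dropout rate of 20"% appears once, to raise the sample size for the clearance endpoint. It is not split by arm, visit or reason.

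**The concern.** Intention-to-treat has two parts: patients are analysed in the arm to which they were randomised, and all randomised patients count. The plan covers the first and is silent on the second. A patient with no score at the visit simply leaves a t test, and that is harmless only if the missing scores would have resembled the observed ones.

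There is reason to doubt this here. The trial's hypothesis is that clearance improves pain and quality of life, and the planned failure rates differ threefold between arms (10% versus 30%). If response also depends on clearance, the observed groups no longer have the case mix that randomisation produced. These outcomes make up the second specific aim and three of the five major secondary endpoints listed in Section 2, and their result would be reported as intention-to-treat.

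**Working it through.** **1. The plan's own sample size.** Inputs from the Power analysis: clearance 70% versus 90%, two-sided alpha 0.05, power 80%. With pooled variance and no continuity correction:

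n = [1.960 × √(2 × 0.8 × 0.2) + 0.842 × √(0.7 × 0.3 + 0.9 × 0.1)]² / 0.2² = 61.6, so 62 per arm and 124 in total, as stated.

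Then 62 × 1.2 = 74.4, so 75 per arm and 150 in total, as stated. No SD or effect size is given for PANQOL, VAS or opiate dose, so what follows is in SD units or relative terms.

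**2. Precision.** The detectable standardised difference at 80% power is (1.960 + 0.842) × √(2/n).

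- n = 75 per arm: 0.46 SD
- n = 60 per arm (75 × 0.8): 0.51 SD

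The 20% is borrowed from the clearance endpoint as an illustration. Questionnaire loss may be lower or higher.

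**3. Bias.** Assume the arm difference acts through clearance. The full difference is then proportional to 0.90 − 0.70 = 0.200. Let a be the dropout in cleared patients and b the dropout in uncleared patients, the same in both arms. Average clearance is 0.8, so holding overall dropout at 20% requires 0.8a + 0.2b = 0.20. The cleared share among responders in an arm with clearance p is

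p(1 − a) / [p(1 − a) + (1 − p)(1 − b)].

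The values of a and b are assumptions; the document gives none.

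| Uncleared b | Cleared a | PPL share | ESWL share | Difference | Against 0.200 |
|---|---|---|---|---|---|
| 50% | 12.5% | 0.940 | 0.803 | 0.137 | −32% |
| 40% | 15% | 0.927 | 0.768 | 0.160 | −20% |
| 30% | 17.5% | 0.914 | 0.733 | 0.181 | −10% |
| 20% | 20% | 0.900 | 0.700 | 0.200 | 0 |
| 10% | 22.5% | 0.886 | 0.668 | 0.218 | +9% |
| 0% | 25% | 0.871 | 0.636 | 0.235 | +17% |

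Loss that is selective in one arm can do more. If all PPL failures were lost while ESWL loss was random, the difference would be 1.00 − 0.70 = 0.300.

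**4. If only cleared patients are surveyed.** This is the literal reading of the PANQOL sentence in Section 3. Both cleared shares are then 1, so the part of the difference that acts through clearance is 0. Expected numbers before any dropout are 75 × 0.9 = 67.5 versus 75 × 0.7 = 52.5, selected on a post-randomisation outcome that differs by arm.

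**5. How much a model can recover.** This was simulated with 75 per arm, SD 2.5, correlation 0.6 between visits, a true difference of 0.40 VAS points and the 40%/15% dropout pattern, all assumed. The observed-case estimate averages 0.32. Using earlier visits gives 0.39 when all five are observed in those who drop out, 0.37 when one is, and no gain when none is.

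**The case against.** **A reader might infer that the comparison is pulled towards no difference.** The document does not support that. Nothing in it says that uncleared patients respond less. Cleared, pain-free patients could equally stop answering, and the table then moves the other way. Section 3 also allows cross-over or combined treatment after failure, so some patients counted as failures may be cleared before or during follow-up, and the 90%/70% mixture overlooks that.

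**A reader might also infer that a fifth of questionnaires are expected to be missing.** The 20% is a sizing allowance for clearance. The reminders and contact attempts are a real effort to keep non-response down, and daily opiate use is to be recorded without being clearly a questionnaire item. These points limit how much is missing; they do not say how it is analysed.

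**Completers-only would be too strong a label.** A t test at a visit drops those missing at that visit, and no visit is named. A t test could also be run on imputed data, but the plan provides for no imputation, so the test as written runs on observed values.

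**The effect may be small.** If cleared and uncleared patients differ by 1 SD, the 40%/15% case shifts the estimate by 0.20 − 0.16 = 0.04 SD, against a standard error of √(2/60) = 0.18 SD. That is fair, and it rules out alarm. It does not justify leaving the method unstated when the scheduled visits already collect what a better one needs.

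**Conclusion.** The point holds in a limited form. The analysis called intention-to-treat is, as specified, an observed-case comparison with no rule for missing scores. The loss of precision is certain whenever scores are missing: 0.46 to 0.51 SD at 20% loss. Bias is conditional on non-response being related to outcome. Over the patterns tabulated it runs from −32% through zero to +17% of the difference, and it can exceed that range if loss is selective in one arm or if only cleared patients are surveyed. Those figures rest on the planned clearance rates, on an effect acting wholly through clearance, and on assumed dropout. They show sensitivity and do not forecast a direction. The two statements about who is surveyed conflict and need to be reconciled first, because no analysis can restore the randomised comparison if failures have no scores. This should be corrected, but it concerns secondary outcomes and leaves the test of the primary endpoint untouched.

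**What to change.** In Section 9, make the main between-arm analysis of PANQOL, VAS and opiate dose one of these:

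- a repeated-measures mixed model with treatment, visit and their interaction, using baseline and every observed visit for all randomised patients; or
- multiple imputation within arm from baseline, all observed visits and, where enough uncleared patients have scores, clearance status. In the PPL arm that may be few: at 40% dropout, 75 × 0.10 × 0.60 = 4.5 expected.

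Keep the observed-case t test as a sensitivity analysis, and add one that allows scores to be missing not at random. In Section 3, reconcile the PANQOL sentence with the partial-clearance subgroup in Section 9, so that every randomised patient is surveyed whether or not clearance is achieved.

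The cost is SAP wording, a clarification of the survey schedule and a little more programming. Either method assumes scores are missing at random given the observed data, which is weaker than what the t test needs. Recovery is only partial for patients with no post-baseline score.

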COMIRB 19-0402

PI: [name]

Version Date: December 6, 2023

SARC Approved 5/8/2019

***Per-oral Pancreatoscopy-guided Lithotripsy vs. Extracorporeal Shock Wave
Lithotripsy For Treating Symptomatic Main Pancreatic Duct Stones in Chronic
Pancreatitis: A Multicenter Randomized Clinical Trial***

Lead Site: University of Colorado

Version Date: December 6, 2023

Table of Contents

Table of Contents.....	2
Synopsis	3
List of Abbreviations	4
Study Protocol.....	5
Research Questions and Hypothesis	5
Basic Design of the Study	7
Sample and Methodology	7
Subject Inclusion and Exclusion Criteria	9
Inclusion Criteria:	9
Exclusion Criteria:	9
Study Steps	10
Screening/Baseline Evaluation	10
Consent	10
Randomization	10
Treatment Regimens	10
Outcome Determination	11
Standard of Care/Research Procedure.....	12
Subject and Study Stopping Criteria.....	12
Data Collection Tool	13
Data Analysis Plan	13
Data and safety monitoring plan.....	14
Definition of AEs, serious AEs, and unanticipated problems	14
Procedures for documentation of adverse events	15
Monitoring of Data	16
Feasibility/Recruitment Plan/Materials	16
Training Plan.....	16

Synopsis

Title	Per-oral Pancreatoscopy-guided Lithotripsy vs. Extracorporeal Shock Wave Lithotripsy in Chronic Pancreatitis: A Multicenter Randomized Clinical Trial
Investigative sites	University of Colorado The Ohio State University Baylor St. Luke's Medical Center Methodist Dallas Medical Center University of Minnesota University Health, San Antonio Indiana University Washington University School of Medicine
Hypothesis	The central hypothesis is that per-oral pancreatoscopy- guided lithotripsy is superior to extracorporeal shock wave lithotripsy in clearance of main pancreatic duct stones, thereby improving pain levels and quality of life in patients with chronic calcific pancreatitis.
Primary Objective	To demonstrate the superiority of per-oral pancreatoscopy over extracorporeal shock wave lithotripsy in clearance of main pancreatic duct stones in patients with chronic pancreatitis. Failure to remove any or all stones with the initial intervention will be an outcome recorded for the study.
Secondary Objective	To demonstrate the effect of stone clearance to reduce pain and opiate use and improve quality of life.
Timeline	Enrollment will be performed over a 24-month time period with follow-up performed at 1, 3, 6, 12, 18, and 24 months after ductal clearance.

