Therefore, our long-term goal is to determine the optimal treatment regimen for chronic pancreatitis-related pain associated with main pancreatic duct stones. Our overall objectives in this application, which is the next step toward attainment of our long-term goal, are to (i) determine whether PPL is superior to ESWL in removing main pancreatic duct stones, and (ii) ascertain the effectiveness of PPL or ESWL in improving pain and quality of life. Our central hypothesis is that PPL is superior to ESWL in removing difficult PD stones, thereby improving pain levels and quality of life in patients with chronic calcific pancreatitis. Our hypothesis has been formulated based on previous retrospective studies from our group demonstrating a higher stone clearance rate with PPL compared to published stone clearance rates for ESWL.^{6,13,14,16,17} The rationale for this project is that the determination of the superior lithotripsy method and its effect on pain and quality of life is likely to guide clinical decision-making in patients with PD stones whereby optimal strategies for the treatment of chronic pancreatitis can be developed. To attain the overall objective, the following two specific aims will be pursued:

1. **Perform a multicenter randomized clinical trial to compare the efficacy of per oral pancreatoscopy-guided lithotripsy with extracorporeal shock-wave lithotripsy in the removal of pancreatic duct stones.** Based on preliminary data, our working hypothesis is that PPL is superior to ESWL in the clearance of PD stones.
2. **Compare the effect of per oral pancreatoscopy-guided lithotripsy with extracorporeal shock-wave lithotripsy in reducing pain and improving quality of life in patients with chronic pancreatitis.** Based on preliminary data, our working hypothesis is that stone clearance will reduce pain levels, decrease opiate use, and improve quality of life.

At the completion of the proposed research, our expected outcomes are to have determined which lithotripsy method is clinically superior in PD stone removal. We also expect to demonstrate the effect of PD stone removal on pain and quality of life. These results are expected to have an important positive impact because they will provide a strong evidence-based support for endoscopic therapies to ultimately

treat chronic calcific pancreatitis more effectively.

2. Basic Design of the Study

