This study is a multicenter randomized trial comparing per oral pancreatoscopy-guided lithotripsy (**PPL**) using either laser lithotripsy (**LL**) or electrohydraulic lithotripsy (**EHL**) with extracorporeal shock wave lithotripsy (**ESWL**) in removing main pancreatic duct (**PD**) stones from patients with chronic calcific pancreatitis. Specific aims for this trial include:

- **SA1:** To determine whether PPL is more effective than ESWL in removing PD stones in terms of main pancreatic duct stone clearance rate in patients with chronic calcific pancreatitis.
- **SA2:** Evaluate the effectiveness of main pancreatic duct stone removal in reducing pain and improving quality of life in patients with chronic calcific pancreatitis.
 - **SA2a:** To determine whether a greater clearance of PD stones via PPL or ESWL will improve quality of life to a greater extent.
 - **SA2b:** To determine whether a greater clearance of PD stones via PPL or ESWL will reduce pain and opiate requirements to a larger extent.

The primary endpoint of this trial will be complete clearance of main PD stones in eligible patients. This study will be statistically powered to detect superiority of PPL over ESWL in this primary endpoint. Major secondary endpoints will include: 1) change in quality of life after PD stone removal; 2) change in pain levels after PD stone removal; 3) change in opiate use after PD stone removal; 4) comparison of total number of procedures in both arms, and 5) PD stone recurrence rate.

3. Sample and Methodology

We will enroll 150 subjects (**Figure 1**) with chronic pancreatitis who have symptomatic main PD stones identified by non-invasive imaging, endoscopic ultrasound or prior endoscopic retrograde pancreatography (**ERP**).

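### The secondary objective is worded as the effect of stone clearance on pain, opiate use and quality of life, but no specified analysis takes clearance status as the exposure

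*Combined protocol and SAP*

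**What the plan says.** The documents word the secondary question in two ways.

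**As an effect of clearance.** The Synopsis gives the Secondary Objective as "To demonstrate the effect of stone clearance to reduce pain and opiate use and improve quality of life". In Section 1, under Aim 2, "our working hypothesis is that stone clearance will reduce pain levels, decrease opiate use, and improve quality of life", and the expected outcomes state: "We also expect to demonstrate the effect of PD stone removal on pain and quality of life". Section 2 does the same in SA2 and its two parts; SA2a, for example, reads "To determine whether a greater clearance of PD stones via PPL or ESWL will improve quality of life to a greater extent".

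**As a comparison of modalities.** The heading of Aim 2 in Section 1 is "Compare the effect of per oral pancreatoscopy-guided lithotripsy with extracorporeal shock-wave lithotripsy in reducing pain and improving quality of life".

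Section 9 then lists four analyses of these outcomes:

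- Between arms, by intention to treat: "change in PANQOLI scores, VAS scores, and opiate daily doses will be compared between subjects in the PPL group and ESWL group".
- A per-protocol version, which attributes outcomes after cross-over to the set of treatments that achieved technical success.
- "A subgroup analysis will also be performed on patients who achieved only partial stone clearance", on the same outcomes.
- Within arms: "Paired t tests will be performed to evaluate individual changes within each arm".

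The only regression in Section 9 has technical success as its outcome, not as its exposure.

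**The concern.** An objective about clearance needs a contrast between patients who clear and patients who do not, and none of the four analyses defines one. The arm comparison contrasts assigned modalities, and most patients in both arms are expected to clear. The per-protocol version sorts patients by treatments received. The subgroup has no stated comparator. The paired tests pool cleared and uncleared patients within an arm and have no control.

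Two errors of interpretation become possible. A significant before-after change could be reported as meeting the Synopsis objective, although it may reflect regression to the mean or the rest of the endoscopic care. All patients receive an ERP (Section 5.5), and Section 1 itself credits stenting of strictures with improving pancreatic juice flow. Conversely, a null arm comparison could be taken to mean that clearance does not matter, when the comparison had little chance of showing that it does.

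**Working it through.** **1. The plan's own figure.** Inputs from Section 9, power analysis: 70% and 90% clearance, two-sided alpha 0.05, power 80%. With pooled variance under the null:

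n per arm = [1.96 × √(2 × 0.8 × 0.2) + 0.842 × √(0.21 + 0.09)]² / 0.20² = (1.109 + 0.461)² / 0.04 = 61.6, so 62 per arm and 124 in total. This reproduces the stated size. Of the 150 enrolled, 20% dropout leaves 150 × 0.80 = 120, or 60 per arm. That number is used below.

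**2. How much of a clearance effect reaches the arm comparison.** Suppose clearance shifts the outcome by d SD and modality acts only through clearance. Then

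expected arm difference = (0.90 − 0.70) × d = 0.20 d.

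The documents give no SD or target effect for PANQOL, VAS or opiate dose, so d is an assumption, shown over a range. For a two-sample t test with 60 per arm, the noncentrality is 0.20 d × √(60/2) = 1.095 d on 118 degrees of freedom. For a cleared versus uncleared contrast the expected groups are 54 + 42 = 96 cleared and 6 + 18 = 24 not cleared, and the noncentrality is d × √(96 × 24 / 120) = 4.38 d.

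| d (SD) | Arm difference (SD) | Power, arm comparison | Power, cleared vs uncleared |
|---|---|---|---|
| 0.3 | 0.06 | 6% | 26% |
| 0.5 | 0.10 | 8% | 58% |
| 0.8 | 0.16 | 14% | 94% |
| 1.0 | 0.20 | 19% | 99% |

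The smallest arm difference detectable with 80% power is 0.52 SD, which would need d = 0.52 / 0.20 = 2.6 SD. Allowing for the extra spread from mixing cleared and uncleared patients, SD = √(1 + 0.15 d²), lowers the 19% to about 17%. Cross-over after failure, which Section 3 allows, could shrink the 20-point contrast further. The last column is not randomised, so its power is power to detect an association.

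**3. Paired tests when treatment does nothing.** Suppose patients enrol e SD above their usual pain and the retest correlation is r (both assumed). The expected fall is e(1 − r), the SD of change is √(2(1 − r)), and the standardised change is e√((1 − r)/2). With n = 60 the noncentrality is that value × √60. For e = 1 and r = 0.5 it is 0.5 × 7.75 = 3.87.

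| Excess at enrolment (SD) | r = 0.5 | r = 0.6 | r = 0.8 |
|---|---|---|---|
| 0.25 | 16% | 14% | 9% |
| 0.5 | 48% | 40% | 23% |
| 1.0 | 97% | 93% | 67% |

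The entries are the share of trials with p < 0.05 in one arm.

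**4. The partial-clearance subgroup.** Section 3 defines partial clearance as removal of more than 50% but less than 100%. By that definition the subgroup leaves out patients with 50% or less removed. (Another sentence in Section 3 uses the term for any removal short of all.) The sentence in Section 9 on tests that follows the subgroup does not say whether partial is compared with complete clearance or PPL with ESWL inside the subgroup.

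**5. Whether the data will exist.** Section 3 introduces the PANQOL schedule as following complete stone removal, and the Synopsis timeline counts follow-up from ductal clearance. The text states no starting point for a patient who never clears.

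**The case against.** Several stronger readings are tempting, and the documents do not support them.

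- *The plan only compares arms and runs before-after tests.* It also has the per-protocol analysis and the partial-clearance subgroup. Neither is a defined clearance contrast, but both are there.
- *The subgroup is analysed without reference to complete clearers.* The comparator is unstated, and a partial versus complete comparison may be intended. The supportable criticism is that it is not specified.
- *The trial cannot answer its secondary objective.* The heading of Aim 2 is a modality comparison, and the planned arm comparison answers it. The defect is that the aim is worded in two ways and the analysis fits only one.
- *The arm comparison can say nothing about clearance.* If modality acts only through clearance, a randomised difference is an unconfounded signal, and arm could serve as an instrument. The plan does not propose this, and step 2 shows how weak the signal would be. The limitation is low information, not impossibility.
- *The paired tests will nearly always be falsely positive.* The 67-97% range needs an enrolment excess of 1 SD. Section 4.1 requires abdominal pain but sets no score threshold and no flare, so smaller excesses are credible.
- *Uncleared patients will not be followed.* The subgroup analysis and the cross-over rule for surveys imply that some of their data are expected. What the text lacks is a schedule for them. Figure 1 is not available in the text reviewed.

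It is also fair to say that Section 9 does not call the paired tests a test of clearance. That link would come from the objective's wording, which is why the wording matters. What stands is that no analysis with clearance status as the exposure is specified for these outcomes.

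**Conclusion.** The concern holds as a mismatch between the clearance-worded objective and the specified analyses. On the plan's own rates the randomised comparison carries one fifth of a clearance effect, with about 8% power for a 0.5 SD effect and 19% for 1 SD (60 per arm, effect acting only through clearance). The paired tests are uncontrolled. Their chance of significance with no treatment effect runs from 9% to 97% over the assumed inputs, so a significant result would not by itself point to clearance. These effect sizes, enrolment excesses and correlations are assumptions; the 90%, 70%, 20% and 150 are the plan's. The point concerns secondary outcomes only. The primary analysis is untouched, and the change should be made before these outcomes are analysed.

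**What to change.** 1. Restate the Synopsis Secondary Objective and SA2, with SA2a and SA2b, to agree with the heading of Aim 2: to compare change in pain, opiate use and quality of life between patients randomised to PPL and to ESWL. Remove from the expected outcomes in Section 1 the claim to demonstrate an effect of stone removal.
2. State in Section 9 that the paired t tests are descriptive and do not support a claim that clearance caused the change.
3. Add one regression per outcome, pooled over both arms, with clearance status as the exposure, adjusted for arm and baseline score and reported as an association. Define clearance as achieved within the assigned treatment (Section 3's maximum of 4 sessions), and handle clearance reached after cross-over in a sensitivity analysis. Keep partial clearance as its own category, or state its comparator, and use one definition of it.
4. Amend Section 3 and the Synopsis timeline so that the 1- to 24-month assessments are timed from the end of assigned treatment for all randomised patients, cleared or not. The regression and the intention-to-treat comparison both need those data.

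The cost is a more modest secondary claim, some rewording, one added model per outcome, and a follow-up schedule for uncleared patients. The last item is an operational change as well as a wording change.
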